6.3.3. Study Day and Reference Dates

The safety reference date is the study intervention start date and will be used to calculate study day for safety measures.

The efficacy reference date is [the date of randomization OR the study intervention start date] and will be used to calculate study day for efficacy measures and baseline characteristics, as well as efficacy durations.

The study day is calculated as below:

- Assessment Date = Missing → Study Day = Missing
- Assessment Date < Reference Date → Study Day = Assessment Date – Ref Date
- Assessment Date ≥ Reference Date → Study Day = Assessment Date – Ref Date + 1

6.3.4. Assessment Window

Protocol assessment window as defined in protocol Section 1.3 will be followed for the statistical analysis.

6.3.5. Handling of Partial Dates

Element	Reporting Detail		
General	
 Partial dates will be displayed as captured in participant listing displays. However, where necessary, display macros may impute dates as temporary variables for sorting data in listings only. In addition, partial dates may be imputed for 'slotting' data to study phases or for specific analysis purposes as outlined below. Imputed partial dates will not be used to derive study day, time to onset or duration (e.g., time to onset or duration of adverse events), or elapsed time variables (e.g., time since diagnosis). In addition, imputed dates are not used for deriving the last contact date in overall survival analysis dataset. 		
Adverse Events	
 Partial dates for AE recorded in the CRF will be imputed using the following conventions: 
 
 Missing start day	 
If study intervention start date is missing (i.e. participant did not start study intervention), then set start date = 1st of month.
 
Else if study intervention start date is not missing:
 
 If month and year of start date = month and year of study intervention start date, then 	
 
 	Missing start day	
If study intervention start date is missing (i.e. participant did not start study intervention), then set start date = 1st of month.
 
Else if study intervention start date is not missing:
 
 If month and year of start date = month and year of study intervention start date, then
Missing start day	
If study intervention start date is missing (i.e. participant did not start study intervention), then set start date = 1st of month.
 
Else if study intervention start date is not missing:
 
 If month and year of start date = month and year of study intervention start date, then 		

Element	Reporting Detail	
		
 – If stop date contains a full date and stop date is earlier than study intervention start date, then set start date= 1st of month. – Else set start date = study intervention start date. 
Else set start date = 1st of month.

	Missing start day and month	
If study intervention start date is missing (i.e. participant did not start study intervention), then set start date = January 1.
 
Else if study intervention start date is not missing:
 
 • If year of start date = year of study intervention start date, then 
 – If stop date contains a full date and stop date is earlier than study intervention start date, then set start date = January 1. – Else set start date = study intervention start date. 
Else set start date = January 1.

	Missing end day	A '28/29/30/31' will be used for the day (dependent on the month and year).
	Missing end day and month	No Imputation
	Completely missing start/end date	No imputation
Concomitant Medications/Medical History	
 • Partial dates for any concomitant medications recorded in the CRF will be imputed using the following convention: 	
	Missing start day	
If study intervention start date is missing (i.e. participant did not start study intervention), then set start date = 1st of month.
 
Else if study intervention start date is not missing:
 
 • If month and year of start date = month and year of study intervention start date, then 
 – If stop date contains a full date and stop date is earlier than study intervention start date, then set start date= 1st of month. – Else set start date = study intervention start date. 
Else set start date = 1st of month.

	Missing start day and month	
If study intervention start date is missing (i.e. participant did not start study intervention), then set start date = January 1.
 
Else if study intervention start date is not missing:
 
 • If year of start date = year of study intervention start date, then 
 – If stop date contains a full date and stop date is earlier than study intervention start date, then set start date = January 1. – Else set start date = study. intervention start date. 
Else set start date = January 1.

Element	Reporting Detail	
	Missing end day	A '28/29/30/31' will be used for the day (dependent on the month and year).
	Missing end day and month	A '31' will be used for the day and 'Dec' will be used for the month.
	Completely missing start/end date	No imputation
Age	Age is derived using the date of first dose. When first dose date is missing, the ICF date is used. Only year of birth is collected so Day and Month of birth are imputed as 30 June. Formula for deriving age is the integer component of: (First Dose Date – 30 Jun of collected birth year +1)/365.25	

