8.1.2. Medical and Vaccination History

Obtain the participant's medical history by interviewing the participant and/or review of the participant's medical records. Record any pre-existing conditions, signs and/or symptoms present prior to the first dose of study intervention in the eCRF.

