6.1.4. Prior and Concomitant Medications

Prior and Concomitant medications will be coded using WHO Drug dictionary version on or after Global B3 Sept 2023.

Multi-ingredient term concomitant medications will be presented according to their combination ATC classification rather than the classifications of the preferred term.

A concomitant medication will be summarized (number and percentage) by ATC 1 and ingredient for FAS in each period (pre/on/post) in which it was taken, so a concomitant medication that was started in the screening and stopped during active treatment will appear in both the pre-treatment and the on-treatment tables.

Concomitant medications include any medication that was taken at some point during the on-treatment period as defined in Section 6.9 of the protocol.

Participants listing of concomitant medication will also be generated for FAS.

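### Concomitant medication with a year-only start and a month-and-year stop before dosing is given a start date after its own stop date (SAP 6.3.5)

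*SAP*

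**What the plan says.** SAP 6.3.5 has a block of rules for partial medication dates. When start day and month are both missing, the branch is entered by "If year of start date = year of study intervention start date, then". Inside it, the protective rule is "If stop date contains a full date and stop date is earlier than study intervention start date, then set start date = January 1". Every other case falls to the default, "Else set start date = study intervention start date" (printed in this branch with a stray full stop). A year-only start in another year goes to 1 January of that year: "Else set start date = January 1". When only the start day is missing, the logic is the same, with "If stop date contains a full date and stop date is earlier than study intervention start date, then set start date= 1st of month" as the protective rule.

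Stop dates are imputed separately. A missing day becomes the last day of the recorded month, and a missing day and month become 31 December.

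The general row says what the imputed dates are for: "partial dates may be imputed for 'slotting' data to study phases". Listings show dates as captured, and imputed dates are not used for study day or duration. SAP 6.1.4 tabulates each drug in every period in which it was taken, so that "a concomitant medication that was started in the screening and stopped during active treatment will appear in both the pre-treatment and the on-treatment tables". SAP 6.3.2 defines pre-treatment as strictly before the first dose of period 1.

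**The concern.** The start rule and the stop rule use different information. The start rule asks whether the drug ended before dosing but accepts only a full stop date as evidence. The stop rule then gives a month-level stop a definite date, which may lie well before dosing. Nothing reconciles the two, so one record can receive a start later than its stop.

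At stake is the reliability of the pre/on/post medication tables. The SAP does not say whether slotting uses the start date alone or the overlap of start and stop with each period. On start date alone, a finished drug appears as on-treatment use. On overlap, it belongs to no period and disappears from the tables. Its correct place under SAP 6.1.4 is pre-treatment only. Protocol 6.9 restricts medication from 30 days before admission, so a spurious on-treatment entry could be mistaken for a breach.

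**Working it through.** The documents give no figure to reproduce; the check is date logic. First-dose dates are not in the documents, so those below are assumed.

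**One record.** First dose 2 September 2024; drug recorded as start 2024, stop March 2024.

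1. The start year equals the first-dose year, so the branch applies.
2. The stop is not a full date, so the protective rule fails and the start becomes 2 September 2024.
3. The stop has a missing day, so it becomes 31 March 2024.
4. Start minus stop = 30 (April) + 31 (May) + 30 (June) + 31 (July) + 31 (August) + 2 = 155 days.

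No assumption about the true days is needed: any day in March precedes 2 September.

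**All records of this type.** Take every true start/stop pair within the first-dose year, with the start recorded by year only and the stop by month and year, where the stop month ends before the first-dose month begins. If n is the number of days from 1 January to the end of the month before first dose, there are n(n+1)/2 such pairs.

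| Assumed first dose | n | Pairs known to have ended before dosing | Start after stop, current rule | Start after stop, imputed stop tested |
|---|---|---|---|---|
| 15 Aug 2024 | 213 | 213×214/2 = 22,791 | 22,791 | 0 |
| 20 Nov 2024 | 305 | 305×306/2 = 46,665 | 46,665 | 0 |
| 20 Jan 2025 | 0 | 0 | 0 | 0 |

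These counts show which branch fails. They are not expected frequencies.

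**Where the rule does not invert dates.** In the same enumeration there were no inversions when:

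- the stop is a full date. With first dose 15 August 2024, start 2024 and stop 10 March 2024 give a start of 1 January 2024;
- only the start day is missing, because a month-level stop in the first-dose month or later is imputed to a month-end that is not before first dose;
- the stop is known by year only, because it becomes 31 December.

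Starts in an earlier month or year than first dose are not moved to first dose at all.

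**Related case.** A drug truly begun before dosing and still ongoing, with a partial start in the first-dose month (or year, if only the year is known), is dated to first dose. For first dose 15 August 2024 the pre-treatment record is lost for all 14 possible earlier start days when the day is missing, and for all 227 (213 + 14) when day and month are missing. Using the 1st of the month or 1 January for every partial start would recover these. It would also label as pre-treatment every drug truly started on or after first dose: 31 − 14 = 17 start days in the first pattern and 366 − 227 = 139 in the second.

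**The case against.** The strongest reply is that the plan already protects drugs that ended before dosing, and that what remains is rare and descriptive. Much of that stands. A reader might infer that the rule shifts every drug finished before dosing; it does not, because the protective rule handles every full stop date correctly. The failure needs two incomplete dates in a particular pattern, and it cannot occur when first dose falls in January. On-treatment misclassification is only one of the two possible outcomes, since overlap slotting would drop the record instead.

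Three wider readings also fail:

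- **Medical history.** It shares the row heading, and Protocol 8.1.2 asks sites to "Record any pre-existing conditions, signs and/or symptoms present prior to the first dose of study intervention", so a first-dose start looks wrong for it. But SAP 6.1.5 plans only listings of medical history, and listings show dates as captured.
- **Hormone replacement therapy.** A reader might expect permitted HRT to appear as newly started on Day 1. Starts in earlier years are not moved, imputed dates do not feed study day, and listings are unaffected.
- **Reason for the 30-day restriction.** Neither inclusion criterion 11 nor Protocol 6.9 attributes it to effects on MCC, so the point cannot be tied to the primary endpoint that way.

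The reply does not remove the defect. The inversion follows from explicit rules, and a start after its own stop is wrong under either way of slotting.

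**Conclusion.** The point holds in a narrow form. A year-only medication start in the first-dose year, combined with a stop known to an earlier month of that year, always yields a start after the stop, and a drug known to have ended before dosing is misplaced in the SAP 6.1.4 tables. The 155 days depend on the assumed first-dose date; the inversion itself does not, provided the stop month is over before the first-dose month begins.

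The number of affected records is unknown and is probably small with up to 24 participants. The effect is confined to descriptive medication summaries: neither the definition of the MCC analysis set nor the primary model uses these dates. This is a desirable correction, not an essential one.

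For drugs with a partial start in the first-dose month or year that continue past dosing, there is a tension with SAP 6.1.4. How to date them is a choice of convention with an error on either side, and no change is required.

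**What to change.** In the medication rows of SAP 6.3.5, impute the stop date first. Then drop the requirement that the stop be a full date, so that the condition becomes: *the recorded or imputed stop date is earlier than the first dose of study intervention*. Drugs that meet it get 1 January (or the 1st of the month, where only the day is missing) and are slotted as pre-treatment only. The adverse-event rows can stay as they are.

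The cost is a few words in the SAP and the matching change in the imputation program. Because the imputed month-end is the latest day the drug could have stopped, no drug started on or after first dose is relabelled by this change. It would also help to state whether medication slotting uses the start date alone or start–stop overlap.

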6.3.6. Trademarks

Trademarks of the [GlaxoSmithKline / ViiV Healthcare] Group of Companies
ADVAIR

Trademarks not owned by the [GlaxoSmithKline / ViiV Healthcare] Group of Companies
NONMEM
SAS
WinNonlin

